15.4 Analysis of Secondary Endpoints

Efficacy and tolerability data will be summarized by each secondary endpoint.

Symptom level over time during the treatment period will be graphed for visualization along the three axes of pain, stinging/burning, and itching/pruritus as well as a composite symptom score. Peak symptom level during the treatment period and pain at the end of treatment exposure will be compared between the conventional treatment arm (A), the combination treatment arm B), and the daylight treatment arm (C), with unpaired t-tests.

Percent reduction in the number of actinic keratoses and proportions of patients with partial and complete clearance of actinic keratoses will be presented descriptively and visualized as histograms. We will compare the percent reduction in the number of AKs and the proportions of patients with clearance between the conventional treatment arm (A) and the combination treatment arm B), and between the conventional treatment arm (A) and the daylight treatment arm (C), using unpaired t-tests.

All analyses will be based on the intent-to-treat (ITT) population. In the ITT population, patients will be counted in the treatment group upon randomization, regardless of receiving any dose of study medication. For efficacy analysis, all missing values due to patient early termination from the study will be imputed using last observation carried forward (LOCF) method, as appropriate. For each patient, the Baseline values will be defined as those values recorded at Day 1 prior to dosing. Patients who are lost-to-follow-up after Baseline will be included to the ITT population carrying forward their Baseline values.

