5.2 Secondary Efficacy Endpoints

The secondary efficacy endpoints are efficacy, local skin reaction to treatment, and symptoms and local skin response during follow-up period.

- 1) Efficacy in clearance of AK at 12 weeks:
 - A. percent reduction in number of AKs from baseline to 12 weeks
 - B. proportion of subjects with complete and partial clearance of AKs as described above.
- 2) To determine whether daylight PDT affords, at end of treatment, a reduction in composite local skin reaction

- 3) To determine whether daylight PDT has a faster resolution of composite treatment symptoms and local skin response during days 8, 29, and 84.

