10.2 Visit 2 (Day 1, may be combined with Screening)

Unblinded investigator:

1. Randomization to treatment arms (1:1:1). Investigator will use sequential envelopes with randomly prefilled treatment arms. Envelopes will be filled in batches of three (nine patients) to ensure even allocation between arms during the course of treatment.
2. Perform and record vital signs.
3. Concomitant medications and Adverse Events review.

Blinded investigator:

4. Perform abbreviated physical examination.
5. Perform an AK count
6. Perform a pre-treatment local skin response assessment
7. Curette any hypertrophic AK
8. Application of ALA

Unblinded investigator:

9. Monitor ALA incubation duration depending on treatment arm
10. Light exposure (BLU-U and/or sunlight, depending on treatment arm)
11. Symptom assessment. All subjects will have symptom assessments at 15, 30, 45, 60, and 75 minutes (Table 2).
12. Skindex-16
13. Record any Adverse Events.
14. Photography of treatment area.

Blinded investigator:

15. Perform a post-treatment local skin response assessment

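### Two carry-forward rules with no stated precedence give opposite skin-response results for a subject with no score after Day 1

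*Combined protocol and SAP*

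**What the plan says.** Section 15.4 (and the synopsis, in the same terms) gives two rules for missing data.

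- The rule for efficacy data reads: "all missing values due to patient early termination from the study will be imputed using last observation carried forward (LOCF) method, as appropriate".
- "Patients who are lost-to-follow-up after Baseline will be included to the ITT population carrying forward their Baseline values", where "the Baseline values will be defined as those values recorded at Day 1 prior to dosing".

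Neither sentence names an endpoint, and nothing says which governs a subject to whom both apply. Section 12.1 lists loss to follow-up among the reasons for discontinuation, so the two groups overlap.

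Section 5.2 is broad about what counts as efficacy: "The secondary efficacy endpoints are efficacy, local skin reaction to treatment, and symptoms and local skin response during follow-up period". Its third item is "faster resolution of composite treatment symptoms and local skin response during days 8, 29, and 84".

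On Day 1, section 10.2 has the blinded investigator first "Perform a pre-treatment local skin response assessment" and, at the end of the visit, "Perform a post-treatment local skin response assessment". Each subject who completes that visit therefore has two Day 1 skin grades.

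**The concern.** The resolution endpoint asks how quickly a treatment-induced reaction subsides. Carrying forward a value from before treatment scores a lost subject as already back where they started. Carrying forward the value taken just after treatment scores the same subject as never improving. Neither is a credible estimate of the Day 8, 29 or 84 grade, and the text permits both.

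The direction of the bias depends on which rule is used. Under the Baseline rule, an arm that loses a subject after a bad reaction replaces that reaction with an untreated grade, so the less tolerable arm can look better. Tolerability is the main question of this trial. Section 14 says the investigator will have access to all study data, so a choice left open now could be made after the results are visible.

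**Working it through.** The plan gives no dropout rate and no figure of its own on this point, so there is nothing to reproduce. The check applies both rules to each secondary endpoint and then sizes the gap.

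**Inputs from the documents.** Ten subjects per arm (4.1). No replacement (12.3). Skin response before and after treatment on Day 1, then Days 8, 29 and 84 (9.1.7, 10.2, Appendix I). Symptoms at 15, 30, 45, 60 and 75 minutes, then Days 3, 8, 15, 29 and 84 (9.1.8, 10.3 to 10.7). AK counts at Screening, on Day 1 ahead of ALA application, then Days 8, 29 and 84 (9.1.6, 10.2).

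**Endpoint by endpoint.**

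| Endpoint | Baseline rule | LOCF | Conflict? |
|---|---|---|---|
| Skin-response resolution, no score after Day 1 | Pre-treatment grade | Post-treatment grade held to Day 84 | Yes, opposite extremes |
| Symptom resolution | No scheduled pre-dose score to carry | Last score held (75-minute, or a later call or visit) | Baseline rule cannot be applied |
| AK, lost before Day 8 | Day 1 count, 0% reduction | Same count, 0% reduction | No |
| AK, lost after Day 8 or Day 29 | Day 1 count, 0% reduction | That visit's count used as Day 84 | Yes |
| Skin reaction at end of treatment | Observed on Day 1 | Observed on Day 1 | Does not arise for later loss |

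**Size, proportion resolved.** Let m of 10 subjects have no skin score after Day 1, and let p be the proportion resolved among the other 10 − m.

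- Baseline rule: [(10 − m)p + m] / 10
- LOCF: (10 − m)p / 10
- Difference: m / 10

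With an assumed p of 60%:

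- m = 1: (5.4 + 1)/10 = 64% against 5.4/10 = 54%
- m = 2: (4.8 + 2)/10 = 68% against 4.8/10 = 48%
- m = 3: (4.2 + 3)/10 = 72% against 4.2/10 = 42%

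The gap of 10 points per subject is a maximum. It takes resolved to mean back to the pre-treatment grade, a definition the plan does not supply, and it needs a post-treatment grade above the pre-treatment one.

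**Size, mean score.** The gap per lost subject is (post − pre)/10. Assume nine observed subjects with a Day 8 mean of 4, and one lost subject with a pre-treatment score of 0, a post-treatment score of 8 and a true Day 8 score of 6.

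- True arm mean: (9 × 4 + 6)/10 = 4.2
- Baseline rule: (9 × 4 + 0)/10 = 3.6
- LOCF: (9 × 4 + 8)/10 = 4.4

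The Baseline rule falls below even the observed subjects' mean of 4.0, so losing the worse reactor improves the arm. If every true Day 84 score is 0, LOCF gives 8/10 = 0.8.

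On the composite range of 0–16 stated in section 9.1.7, the gap cannot exceed 16/10 = 1.6 per lost subject. The items do not produce that range: four items graded 0–3 give a maximum of 12, and the six items graded 0–4 in Appendix V give 24. The bound would then be 1.2 or 2.4.

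**Size, AK reduction.** Assume nine completers averaging an 80% reduction. One subject lost before Day 8 gives 9 × 80/10 = 72% under either rule. One subject lost after Day 29, with an assumed 80% reduction at that visit, gives 72% under the Baseline rule and (9 × 80 + 80)/10 = 80% under LOCF.

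**The case against.** **Scope.** Section 3.2 attaches efficacy to AK clearance alone, section 15.3 calls symptoms tolerability endpoints, section 15.4 opens by separating efficacy from tolerability, and the imputation text follows the AK paragraph. An AK-only reading is therefore possible. Against it, section 5.2 puts all three items under secondary efficacy endpoints and section 15.4 exempts none. If the AK-only reading were intended, follow-up skin response and symptoms would have no missing-data rule at all, and the AK divergence after Day 8 would remain.

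**The Baseline sentence as a special case.** It could be meant only for subjects with no later observation, with LOCF covering everyone else. The text does not say so. On that reading a subject with a post-treatment Day 1 grade falls to LOCF, and the treatment-day reaction is still held to Day 84.

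**Discretion.** The qualifier closing the LOCF sentence leaves room for judgement, but it does not extend to the Baseline sentence and names no alternative.

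**Limited reach.** This part stands. Sections 12.1 and 12.2 ask for an early discontinuation visit, and section 10.8 collects symptoms, AK count and skin response there, so the extreme skin-response conflict is confined to subjects with no skin score after Day 1. Day 3 and Day 15 calls give later symptom scores. No between-arm test is specified for follow-up skin response or symptoms, and the study calls itself small and descriptive.

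**Stronger readings to avoid.** A reader might infer that every secondary efficacy endpoint is imputed as either fully resolved or never resolving. The documents do not support this. AK loss before Day 8 is non-response under both rules, end-of-treatment skin reaction is observed on Day 1, and the Baseline rule has no scheduled symptom value to carry. Nor does the Baseline rule imply a skin score of 0, because the pre-treatment grade may be higher. The documents also do not say that a Day 8 AK count is distorted by the skin reaction.

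**Conclusion.** The point holds for the Day 8, 29 and 84 resolution endpoint and, more narrowly, for AK counts. For skin response, the two written rules give opposite answers for any subject with no score after Day 1, with no precedence stated. Each such subject is worth up to 10 percentage points of an arm's proportion resolved, and the Baseline rule can reward an arm for losing its worst reactors. For symptoms, one rule freezes the last score and the other cannot be executed from scheduled data. For AK counts, the rules part only when loss follows Day 8 or Day 29.

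The 10-point figure follows from the arm size and the definition of resolved given above. The example means and percentages rest on assumed scores and numbers lost. The documents give no dropout rate, so the actual effect is unknown, and it is nil if every subject is seen at every visit.

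**What to change.** Section 15 promises a detailed SAP before the final analysis, so this can be settled there, before anyone looks at follow-up data by arm.

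- **Skin response and symptoms:** do not carry values forward. Analyse all observed visits by arm and day, for example with a repeated-measures mixed model kept simple for 10 subjects per arm. The exact model is optional; stating one rule is not.
- **AK clearance:** score a missing Day 84 as not cleared.
- **AK percent reduction:** name one primary approach. The same repeated-visit analysis, with the baseline count included, would serve.
- **Sensitivity:** keep LOCF and Baseline carry-forward only here, showing both extremes where both can be computed, with the number of subjects imputed in each arm.

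The cost is SAP wording and slightly more analysis work. No visit or assessment needs to be added.

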15.5 Interim Analysis

Not applicable.

15.6 Sample Size and Randomization

This is a small descriptive study. With ten subjects in each group, we will be powered to detect a 1.25-point difference in pain (pain scale 1-10) with a two-sided alpha of 0.05 and a power of 0.8.

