1 BACKGROUND

Photodynamic therapy (PDT) is one field therapy option for the treatment of actinic keratosis (AK). PDT involves the topical application of aminolevulinic acid (ALA), or one of its derivatives, as a photosensitizing agent. In response, rapidly proliferating, dysplastic cells preferentially accumulate protoporphyrin IX (PpIX). When PpIX is activated by blue or red light, singlet oxygen species are produced, resulting in cell death. PDT is beneficial due to its brief treatment course, ease of patient compliance, and efficacy in clearing AK. However, its main drawbacks are the adverse effects of pain, burning, pruritus, erythema, crusting, and inflammation associated with treatment. Daylight PDT, when compared with conventional PDT, has been associated with significantly less pain while achieving comparable efficacy for the treatment of AK in randomized trials from Nordic countries and Australia.¹⁻²

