4 STUDY DESIGN

4.1 Study Overview

This is a randomized (1:1:1) controlled trial with parallel group design. Thirty adult subjects are planned; with 10 subjects in each of three treatment arms.

Screening data will be reviewed to determine subject eligibility. Subjects who meet all inclusion criteria and none of the exclusion criteria will be entered into the study.

The following medications and devices will be used:

- (1) Aminolevulinic acid HCl topical solution 20% (Levulan Kerastick)
- (2) BLU-U blue light phototherapy illuminator

Three treatment arms to be compared are as follows:

- A. Conventional arm:** Acetone preparation, ALA topical application, 1 hour incubation, 16:40 BLU-U exposure, application of sunscreen.
- B. Combination arm:** Acetone preparation, ALA topical application, 15 minute incubation, 16:40 BLU-U exposure, application of sunscreen, 45 minute daylight exposure.
- C. Daylight arm:** Acetone preparation, ALA topical application, 15 minute incubation, application of sunscreen, 1 hour daylight exposure.

Total duration of subject participation will be up to 115 days. Total duration of the study is expected to be 16 months.

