9.1.8 Symptom assessment

The patient symptom assessment will measure three axes: pain, stinging/burning, and itching/pruritus. Each of these three will be scored by patient report on a numeric scale (0= none, 10= worst possible). Each symptom will be scored and a composite score will be calculated (range 0-30). All subjects will have symptom assessments at 15, 30, 45, 60, and 75 minutes (Table 2). These times allow equivalent assessments relative to medication application regardless of treatment protocol.

A Universal Pain Assessment Tool demonstrating the numeric scale, verbal descriptor scale, and activity tolerance scale will be provided to assist patients in selecting their pain level (Appendix IV).

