15 STATISTICAL METHODS AND CONSIDERATIONS

Prior to the analysis of the final study data, a detailed Statistical Analysis Plan (SAP) will be written describing all analyses that will be performed. The SAP will contain any modifications to the analysis plan described below.

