15.3 Analysis of Primary Endpoint

This is a small descriptive study, with the primary tolerability endpoints: 1) peak symptom level and composite score during the treatment period and 2) symptom level and composite score at the end of treatment exposure.

Symptom level over time during the treatment period will be graphed for visualization along the three axes of pain, stinging/burning, and itching/pruritus as well as a composite symptom score. Peak symptom level during the treatment period and pain at the end of treatment exposure will be compared between the conventional treatment arm (A), the combination treatment arm B), and the daylight treatment arm (C), with unpaired t-tests.

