APPENDIX IV. UNIVERSAL PAIN ASSESSMENT TOOL

UNIVERSAL PAIN ASSESSMENT TOOL

This pain assessment tool is intended to help patient care providers assess pain according to individual patient needs. Explain and use 0-10 Scale for patient self-assessment. Use the faces or behavioral observations to interpret expressed pain when patient cannot communicate his/her pain intensity.

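### Does the 80% power stated for a 1.25-point pain difference with 10 per arm fail because the plan gives no standard deviation?

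*Combined protocol and SAP*

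**What the plan says.** The sample-size rationale is the same in Section 15.6 and the synopsis. After describing the study as small and descriptive, it continues: "With ten subjects in each group, we will be powered to detect a 1.25-point difference in pain (pain scale 1-10". The error rates attached to this are a 5% two-sided significance level and 80% power. Section 4.1 (Study Overview) gives the matching enrolment, "with 10 subjects in each of three treatment arms".

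Section 15.3 (Analysis of Primary Endpoint) opens with the same descriptive label. It then has peak symptom level and end-of-exposure pain "compared between the conventional treatment arm (A), the combination treatment arm B), and the daylight treatment arm (C), with unpaired t-tests".

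No SD, standardised effect or source for the variability of the pain score appears in the documents. Section 15 announces a detailed statistical analysis plan (SAP) before the final analysis: "The SAP will contain any modifications to the analysis plan described below".

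The pain score itself is defined in Section 9.1.8 on a "numeric scale (0= none, 10= worst possible" basis, and Appendix IV instructs staff: "Explain and use 0-10 Scale for patient self-assessment".

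**The concern.** A power claim in points needs four inputs besides the test: the number per arm, the significance level, the difference and the SD. Three are given and the SD is not. Yet the claim is worded as a fact about the design, and it is the only sample-size figure in the plan.

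If the true spread were well above 1 point, 10 per arm could detect only a much larger difference than 1.25. A reader relying on Section 15.6 might then take a non-significant comparison as evidence against a difference of that size. Section 15.3 does not mention confidence intervals, so the plan offers no other statement of precision.

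The number 1.25 is also close to what a normal approximation gives with an SD of exactly 1. That raises the suspicion that a standardised effect was written down as points, or that the small-sample t correction was left out.

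**Working it through.** **Inputs.** n = 10 per arm (Sections 4.1 and 15.6); difference 1.25 points, two-sided alpha 0.05 and power 0.80 (Section 15.6); unpaired t-test (Section 15.3). The SD is not given, so every SD below is an assumption.

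**Can the stated figure be reproduced?** Not from the documents' own inputs. The nearest match is the normal approximation with an assumed SD of 1:

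(1.960 + 0.842) × √(2/10) = 2.802 × 0.4472 = 1.253 points.

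That is a possible origin, but not the only one. Solving for the SD that gives 80% power at 1.25 points under other set-ups yields:
- 1.08 for a one-sided t-test;
- 1.11 for 10 against 20 pooled, two-sided;
- 1.26 for a paired or one-sample t-test with n = 10.

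The figure alone does not reveal which SD or method was used.

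**Condition under the planned test.** For 10 v 10 the t-test has 18 degrees of freedom and critical value 2.101. Its noncentrality is (difference/SD) × √(10/2). Power of 0.80 requires difference/SD = 1.325, that is, noncentrality 1.325 × 2.236 = 2.963. Hence the largest SD is 1.25/1.325 = 0.943 points.

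**Power by assumed SD (equal in both arms), from the noncentral t distribution:**

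| Assumed SD (points) | Power for 1.25 points | Difference detectable with 80% power |
|---|---|---|
| 0.75 | 94.1% | 0.99 |
| 0.90 | 83.6% | 1.19 |
| 0.94 | 80.3% | 1.25 |
| 1.00 | 75.3% | 1.32 |
| 1.50 | 42.2% | 1.99 |
| 2.00 | 26.3% | 2.65 |

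**Unequal spread.** With equal arm sizes the pooled variance is the mean of the two arm variances, so the 0.943 limit applies to the root-mean-square SD. Simulation at that value (400,000 runs per setting, SD ratios 2 to 5) gives 79.7% to 79.9% for the pooled test and 75.8% to 78.1% for the Welch version. This moves the limit only slightly. The Background says daylight treatment "has been associated with significantly less pain while achieving comparable efficacy", which concerns the level of pain, not its spread.

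**What the analysis will use.** The t-test takes its SD from the trial data, not from Section 15.6. The 95% interval from the same test has half-width 2.101 × SD × √(2/10) = 0.94 SD. If the observed SD were 2, that would be 0.94 × 2 = 1.88 points, and the imprecision would be plain from the data whatever the planning figure was.

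**Scale label.** A scale of 1-10 or 0-10 enters none of these formulas. Section 9.1.8 and Appendix IV agree on 0-10, so the version used with patients is not in doubt.

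**The case for a change.** The strongest case for acting is that calling the study descriptive does not make an explicit power claim sound. The next sentence still gives a number and Section 15.3 still plans tests. The announced SAP is not said to supply an SD. The correction would be one sentence in two places: state the SD and its source, or give the detectable difference as 1.32 SD. If the SD-of-1 reading is right, the planned test has 75.3% power, 4.7 percentage points short, and 12 per arm rather than 10 would be needed to pass 80%. There is no margin either: Section 12.3 rules out replacing withdrawals and no multiplicity adjustment is stated; at alpha 0.05/3 the SD limit would fall to about 0.79.

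Part of this stands. The statement is conditional on a number the reader cannot see, and naming it would be better documentation. The rest does not carry the point further. The 75% figure rests on a guessed SD that no section mentions. Randomisation, treatment and the 15-to-75-minute symptom scores all fall on Day 1 (Section 10.2), so later withdrawals do not reduce the data for these comparisons. The quoted power is for a single comparison at 0.05, as Section 15.6 states it. Interval estimates come from the same t-tests, and the SAP announced in Section 15 can specify them.

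**Conclusion.** The gap is real but minor, and no change to the plan is needed. The stated power is unverifiable, not shown to be wrong: it is correct for a root-mean-square SD of about 0.94 points or less under the pooled unpaired t-test, and too high above that. How far too high depends wholly on an SD the documents do not give (75% power at 1.0, 26% at 2.0). These figures assume roughly normal scores, 10 evaluable subjects per arm and an unadjusted 5% level.

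Supplying the missing SD would not alter the 30 subjects, the data collected, the t-tests, or any estimate or conclusion drawn from them. In a study presented as small and descriptive, this is missing detail in the rationale, together with a clerical slip in the scale label.
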